When the primary efficacy endpoint is missing, the last observation carried forward (LOCF) principle will be used to populate the primary endpoint, i.e. the Month 3 GOS assessment will be carried forward. In the event that a subject is lost to follow-up and has neither the 3 nor the 6-month GOS, the missing values will be imputed based upon the primary proportional odds model (POM).

To obtain values for the missing responses using the POM the predicted response probabilities will be used. Specifying the PREDICTED option on the OUTPUT statement of PROC LOGISTIC, 3 (number of categories in response variable – 1) predicted probabilities will be provided for each subject; these are the ordered cumulative probability of each response category, i.e.

$$\text{Probability}(Y \leq 1) = P(Y=1) = \text{Probability GOS}=1$$

$$P(Y \leq 2) = \text{Probability that GOS is 1 or 2}$$

$$P(Y \leq 3) = \text{Probability that GOS is 1, 2 or 3}$$

Therefore, to obtain the predicted probability of each individual response, for example, the probability that the response was GOS=2, the following calculation is performed:

$$P(Y=2) = P(Y \leq 2) - P(Y \leq 1)$$

Similarly,

$$P(Y=3) = P(Y \leq 3) - P(Y \leq 2)$$

and finally,

$$P(Y=4) = 1 - [P(Y \leq 3)]$$

since the individual probabilities must sum to one.

The missing GOS response will then be set to the most probable category, i.e. the response with the largest predicted probability.

It is anticipated that there will be minimal missing data, however sensitivity analyses will be carried out to confirm that the imputation method(s) did not have an impact on the primary efficacy analysis results. Therefore, the primary efficacy analyses will also be conducted on observed values only, without any imputation.

Covariates, missing data imputation

For the primary efficacy analyses, missing data for the following covariates will be imputed as the most commonly occurring value over subjects with non-missing data: motor response component of GCS, pupillary response, presence of hypoxia, presence of hypotension, CT classification, and presence of traumatic subarachnoid hemorrhage.

GOS assessment – Dead responses

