Subjects without a GOS response assessment at Month 6 but who have a death date from the Death Report eCRF within 6 months + 28 days of their randomization date (calculated as death date – randomization date + 1 \leq 208) will be assigned a Month 6 GOS response of Dead. Similarly, subjects without a GOS response assessment at Month 3 but who have a death date from the Death Report eCRF within 3 months + 28 days of their randomization date (calculated as death date – randomization date + 1 \leq 118) will be assigned a Month 3 GOS response of Dead.

Secondary Endpoint: Mortality at Month 1

Survival status from the date of injury (Day 1 of the study) until Day 30 (Month 1) will be monitored and recorded as lost to follow-up, consent withdrawn, alive, dead or other. Only subjects with a mortality assessment post-injury of alive or dead will be used in the assessment of mortality.

Secondary Endpoint: Mortality at Month 6

Survival status from the date of injury (Day 1 of the study) until Day 180 (Month 6) will be monitored and recorded as lost to follow-up, consent withdrawn, alive, dead or other. Only subjects with a mortality assessment post-injury of alive or dead will be used in the assessment of mortality.

Time to death

The time to death (in days) will be defined as:

$$\text{Date of death} - \text{date of TBI} + 1$$

If a subject does not die during the conduct of the study, they will be censored at the earliest (minimum) of their Month 6 GOS assessment date and end of study date, and censor time (in days) will be defined as:

$$\text{Minimum(month 6 GOS assessment date, end of study date)} - \text{date of TBI} + 1$$

Since subjects were not followed for death after their Month 6 GOS assessment, subjects who have a death recorded after the assessment will be censored on the date of their Month 6 assessment.

Exploratory Endpoint: CPP

The following formulae are used to derive CPP:

$$\text{Mean Arterial Pressure (MAP)} = \frac{2}{3} \text{ diastolic BP} + \frac{1}{3} \text{ systolic BP};$$

$$\text{CPP} = \text{MAP} - \text{ICP}.$$

MAP will be recorded as missing if either systolic BP and/or diastolic BP measurements are not recorded. CPP will be calculated where MAP and ICP have both been recorded; if either is missing the CPP will be recorded as missing.

Exploratory Endpoint: TIL

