9.5 Efficacy Analyses

9.5.1 Primary Efficacy Analysis

The primary efficacy variable is GOS evaluated at 6 months post injury. The primary analysis will be based on imputation of missing data as described in Section 5.

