9.5.1.1 Proportional Odds Model

The primary efficacy variable of GOS at 6 months post injury will be compared between treatment groups using a POM. For the purposes of this analysis the first two categories of the GOS will be combined (vegetative state and dead). A POM will be fitted including the effect of treatment, geographic region (North America, Europe, Asia, and South America), age, GCS motor score, pupil response, and CT classification. With 4 categories in the response variable, GOS at 6 months following injury, the POM simultaneously fits 3 (number of categories – 1) binary logistic regression models as follows.

If $Y = \text{response} = \text{GOS at 6 months following injury}$.

Model 1

$Y_1 = 0$ (not event), if $Y = \text{vegetative state or dead}$
 $Y_1 = 1$ (event), if $Y = \text{severe disability, moderate disability, good recovery}$

Model 2

$Y_2 = 0$ (not event), if $Y = \text{vegetative state or dead, severe disability}$
 $Y_2 = 1$ (event), if $Y = \text{moderate disability, good recovery}$

Model 3

$Y_3 = 0$ (not event), if $Y = \text{vegetative state or dead, severe disability, moderate disability}$
 $Y_3 = 1$ (event), if $Y = \text{good recovery}$

The dichotomous logistic regression models for Y_J ($J=1, 2, 3$) can be expressed as follows:

$$\ln(P_J/(1 - P_J)) = \alpha_J + \beta_1 X_1 + \beta_2 X_2 + \beta_3 X_3 + \beta_4 X_4 + \beta_5 X_5 + \beta_6 X_6,$$

where

- \ln is the natural logarithm,
- P_J = Probability of an ‘event’ (for example, good recovery) = Probability that $Y_J = 1$,
- $P_J/(1 - P_J)$ = odds of an ‘event’,
- X_1 = treatment group,
- β_1 = effect of treatment,
- X_2 = region,
- β_2 = effect of region,
- X_3 = age,
- β_3 = effect of age,
- X_4 = GCS motor score,
- β_4 = effect of GCS motor score,
- X_5 = pupil response,
- β_5 = effect of pupil response, and
- X_6 = CT classification,
- β_6 = effect of CT classification.

With a POM, it is assumed that the effect of the explanatory variables, such as treatment, are identical for all possible dichotomies of the response variable, that is, β_1 , etc. are the same for each model.

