If the p-value from the test of the null hypothesis of $\beta_1 = 0$ is less than 0.0003 (at the interim) or 0.0098 (at the final analysis), it will be concluded that BHR-100 is statistically significantly different from placebo with respect to the GOS at 6 months following injury. The odds of some degree of improvement in the GOS at 6 months will be modeled and the corresponding common odds ratio for treatment, e^{β_1} , can then be interpreted to determine the direction of the treatment difference as follows. With the placebo group being considered as the reference category, if the odds ratio (OR_{BHR-100/placebo}) is greater than 1, the odds of some improvement in the GOS at 6 months is greater in the BHR-100 treatment group compared to placebo.

In the event that the primary efficacy analysis does not show statistical significance at the study-wise 1% significance level, please refer to section 9.5.1.4 for further details on how the statistical significance of the primary efficacy analysis should be interpreted.

The POM will be fitted in SAS[®] using the PROC LOGISTIC procedure.

Goodness of fit of the model will be assessed using the Deviance and Pearson tests (add SCALE = NONE AGGREGATE to the MODEL statement of PROC LOGISTIC) to compare the fitted model with the saturated model. If these tests are not statistically significant it implies that the model fits the data adequately.

The score test for the proportional odds assumption and individual p-values associated with the tests of effects (treatment, geographic region, age, GCS motor score, pupil response, and CT classification) will be summarized for the POM of GOS at 6 months post injury.

The odds ratios and associated 95% CIs for the levels of the effects relative to a reference category will be presented for all factors and covariates included in the POM of GOS at 6 months post injury.

In addition to the results of the hypothesis tests from the statistical modeling, the number of non-missing observations, absolute and relative frequency (n and percentages), will be provided by treatment group for the GOS categories at 6 months post injury.

The analyses above will be repeated for the straight observed case analysis (no imputation of 6-month GOS or covariates) in the mITT population, the straight observed case analysis in the PP population (no imputation of 6-month GOS or covariates), and the analysis of imputed missing values in the mITT population for US subjects only.

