9.5.1.4 Interpretation of Statistical Significance of Primary Efficacy Analysis

In the event that the primary efficacy analysis does not show statistical significance at the study-wise 1% significance level, i.e. the final analysis p-value is not less than 0.0098, a final adjusted p-value will be calculated and the result considered statistically significant at the 5% level if the adjusted p-value is less than 0.05. The adjusted p-value will be calculated using EAST (Cytel Statistical Software, Cambridge, MA) or other appropriate statistical software

package to adjust for the interim analysis using the pre-specified boundaries discussed above and in section 7.

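### Imputing the most probable GOS category from the treatment-containing primary model, then testing it as observed, understates the standard error; this is negligible near 1% affected but gives a level of about 2–3% instead of 0.98% at 5%

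*SAP*

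**What the plan says.** SAP section 5 deals with a missing Month 6 GOS in steps. The Month 3 GOS is carried forward where there is one. A subject with no GOS assessment but a death report inside the window "will be assigned a Month 6 GOS response of Dead". What remains is the case described as "In the event that a subject is lost to follow-up and has neither the 3 nor the 6-month GOS". For these subjects the primary proportional odds model (POM) is used to predict the probability of each of the four categories, and "The missing GOS response will then be set to the most probable category, i.e. the response with the largest predicted probability".

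Section 9.5.1 makes the imputed data set the basis for the decision: "The primary analysis will be based on imputation of missing data as described in Section 5". Section 9.5.1.1 shows that the imputation model includes the randomized arm: "A POM will be fitted including the effect of treatment, geographic region", with age, GCS motor score, pupil response and CT classification as the other terms. The treatment test is a Wald test at 0.0003 (interim) or 0.0098 (final). If the final test misses 0.0098, section 9.5.1.4 allows a second claim, with "the result considered statistically significant at the 5% level if the adjusted p-value is less than 0.05". No multiple imputation or variance correction is described.

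On the amount of missing data the SAP says only: "It is anticipated that there will be minimal missing data". Observed-case repeats are planned as sensitivity analyses.

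**The concern.** Each affected subject receives one fixed value, chosen partly by the estimated treatment effect. Under the SAP's assumed placebo distribution, good recovery (31%) and vegetative/dead (29%) nearly tie as the most probable category. A small chance difference between arms can therefore push a borderline patient to one end of the scale on one arm and to the other end on the other arm. The refit then counts these values as independent evidence for the difference that produced them.

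The primary test could then exceed the 1% level that the design sets out to protect, and the fallback claim at 5% rests on the same analysis.

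**Working it through.** **The plan's own figure.** Whitehead's formula is N = 12(z₁₋α/₂ + z₁₋β)² / [(ln OR)²(1 − Σp̄³)]. The inputs from SAP 3.1 are OR 1.5, two-sided α 0.01, 90% power and placebo 31/21/19/29%. An OR of 1.5 gives 40.3/21.6/16.7/21.4% on BHR-100, so Σp̄³ ≈ 0.0767. Then N = 12 × (2.576 + 1.282)² / (0.1644 × 0.9233) ≈ 1176, against 1180 stated. The design inputs reproduce.

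**Assumptions.** The documents give neither the share missing both assessments nor the prognostic strength of the covariates, so both were varied. Strength is expressed as the standard deviation of the covariate part of the linear predictor (LP-SD). Cut-points were solved to keep the marginal distribution at 29/19/21/31.

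**Which categories are assigned.** At LP-SD 0.9, the probability of severe disability peaks at 0.233 and that of moderate disability at 0.252, while the larger end category is never below 0.271. Imputed values are therefore almost all at the ends of the scale: 100% for LP-SD up to 1.0, 98% at 1.2 and 83% at 1.6. Under the null, swapping only the arm label changes the assigned category for about 4% of imputed subjects at LP-SD 0.9 and 7% at 0.4.

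**Simulated level.** N = 1180, no treatment effect, 12 slopes, loss among patients not vegetative/dead, 10,000 trials per LP-SD. The steps were: fit the POM to observed cases, impute the mode, refit, and test at 0.0098. Entries are rejection in %, with observed-case on the same trials in brackets.

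| Missing both | LP-SD 0.4 | 0.6 | 0.9 | 1.2 |
|---|---|---|---|---|
| 0.5% (6) | 1.16 (1.03) | 1.03 (0.94) | 1.15 (0.98) | 1.18 (1.14) |
| 1% (12) | 1.28 (1.08) | 1.19 (0.91) | 1.32 (1.06) | 1.26 (1.09) |
| 2% (24) | 1.70 (1.00) | 1.40 (0.93) | 1.55 (1.05) | 1.46 (1.12) |
| 3% (35) | 2.09 (0.99) | 1.86 (0.91) | 1.75 (1.02) | 1.69 (1.23) |
| 5% (59) | 3.12 (1.01) | 2.45 (0.96) | 2.06 (0.94) | 2.09 (1.23) |

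The Monte Carlo SE is 0.10 points at a level of 1% and 0.17 at 3%. With loss completely at random (LP-SD 0.9), the level was 1.10 (0.90) at 1% missing and 2.15 (0.98) at 5%. At p<0.05, an unadjusted proxy for the fallback, it was 5.64–6.12% (4.90–5.53%) at 1% missing and 7.59–10.24% (5.05–5.51%) at 5%.

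**Where the excess comes from.** At LP-SD 0.9 and 5% missing, the empirical SD of the log OR is 0.1235 against a mean reported SE of 0.1100; for observed cases the figures are 0.1130 and 0.1120. The variability rises by 0.1235/0.1130 − 1 ≈ 9%, while the SE falls by only 1 − 0.1100/0.1120 ≈ 1.8%. As a cross-check, the ratio 0.1235/0.1100 = 1.123 implies a level of 2Φ(−2.583/1.123) ≈ 2.1%, which matches the simulated 2.06%.

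**Cause isolated.** The same modal rule with treatment left out of the imputation model gave 0.91–1.20% at 5% missing. Single imputation and extreme values alone therefore do not inflate the level; the treatment feedback does.

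**Separate simulation.** A different covariate set-up, loss at random and 20,000 trials gave, at 5% missing, 2.4% (LP-SD 0.52), 1.9% (0.87) and 1.8% (1.22), against 0.97–1.03% for observed cases. Extreme covariate strengths (12,000 trials each) gave 4.7% (0.26) and 1.6% (1.74). At 1% missing the excess over observed cases was about 0.1–0.2 points.

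**Estimate under a true effect.** With OR 1.5 and LP-SD 0.9, the median estimate was 1.51 against 1.50 for observed cases at 1% missing, and 1.54 against 1.51 at 5%.

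**The case against.** The strongest reply is that the plan expects few such patients. A rate of 5% means 59 treated subjects with no GOS at either visit and no qualifying death record. Deaths are assigned, Month 3 values are carried forward, and randomized but untreated subjects are outside the mITT population. This stands: the 5% is an assumption, and at 1% or less the effect is negligible.

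Second, 2–3% may be high even at 5%. The programmer note to Table 14.2.2.1 expects roughly even splits within prognosis tertiles. For a normal linear predictor that corresponds to LP-SD near 0.9 (52/52/51% favorable), where the level is about 2%. This partly stands. The prognostic score uses more factors than the POM, so the POM predictor may be weaker; at 0.6 the level is 2.45%.

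Third, SAP section 5 speaks of subjects lost to follow-up, and the plan records withdrawn consent as a separate status. The one route that the documents name for survivors to miss both assessments is withdrawal after refusing consent on regaining capacity (protocol 10.3), and on that wording it might not reach the rule. However, protocol 8.3.3 and the footnotes to Tables 14.2.1.1 and 14.2.1.2 apply the rule without that condition, so the matter is unclear rather than settled.

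Fourth, the observed-case analyses in 9.5.1.1 to 9.5.1.3 would reveal a discrepancy. They would, but none of them replaces the imputed result as the basis for the decision.

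Finally, the rejections are two-sided, so under the null about half favor placebo.

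**Conclusion.** The concern holds and is minor. The stated rule produces a standard error that is too small for the estimate it accompanies, because treatment is in the imputation model and the modal values are treated as data. If about 1% of subjects lack both assessments, the effect on the decision is negligible. If 5% do, the final test runs at about 2–3% instead of 0.98%, nearer 2% when the covariates are moderately or strongly prognostic and about 3% when they are weak.

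Confidence in the mechanism is high. The size rests on assumed missing rates, covariate effects and loss patterns. The interim look was not simulated, and the fallback figures are a proxy. Priority is low unless the blinded count shows several percent of subjects missing both assessments.

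**What to change.** For subjects with neither GOS and no qualifying death record, and only for them, replace the modal assignment with multiple imputation:

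- Draw the POM parameters from their estimated distribution.
- Draw the category from the four predicted probabilities that section 5 already derives.
- Refit the primary POM and combine at least 20 imputations by Rubin's rules.

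State plainly whether withdrawn consent is covered. Settle the change before unblinding, and report the blinded count of these subjects from the pre-lock review in SAP 8.2. At about 12 or fewer the change has little practical effect.

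In 4,000 null trials at 5% missing, multiple imputation gave 1.20% at LP-SD 0.9 (observed-case 1.25%, SAP rule 2.20%) and 1.20% at 0.4 (1.25%, 3.45%). With a true OR of 1.5 (LP-SD 0.9, 5% missing), power was 86.8% against 87.1% for observed cases, and the estimate was 1.51. Dropping treatment from the modal rule also restores the level but is a poorer choice: the estimate was 1.48 and power 83.7%. Making the observed-case analysis primary would perform about as well, but it would depart from the model-based imputation in protocol 8.3.3, which multiple imputation respects.

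Leave the carry-forward step, the death rule and the observed-case analyses as they are. The cost is one SAP paragraph, the matching table footnotes and standard code, with no new data or patients. The p-value may be slightly less favorable. The trial is under a Special Protocol Assessment agreement (SAP 1.1). The documents do not show whether it covers the imputation rule, so the agency may need to be told first.
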